9.4.2 Time Period and Frequency for Collecting AE and SAE Information

AEs and SAEs should be documented from the time the subject provides informed consent until subject participation in the trial has been completed.

9.4.3 Identifying AEs and SAEs

AE information may be volunteered by the subject or solicited by trial personnel through non-leading questions. At each visit, after the subject has had the opportunity to spontaneously mention any problems, the investigator should inquire about AEs by asking the standard questions shown below and report as applicable:

- “Have you had any health problems since your last study visit?”
- “Have there been any changes in the medicines you take since your last study visit?”

AEs should be reported for any clinically relevant change, as determined by the investigator, in concomitant medication(s) that is the result of an untoward (unfavorable and unintended) change in a subject's medical health.

In addition, changes in any protocol-specific parameters and/or questionnaires evaluated during the study are to be reviewed by the investigator. Any untoward (unfavorable and unintended) change in a protocol-specific parameter [REDACTED] that is clinically relevant, in the opinion of the investigator, is to be reported as an AE. These clinically relevant changes will be reported regardless of causality.

9.4.4 Recording of AEs and SAEs

All AEs occurring during the trial, regardless of the assumption of causal relationship, must be documented on the respective CRF. Qualified trial staff responsible for assessing AEs will be listed on the Site Authorization and Delegation Log. This includes assessment of AE severity and relationship to treatment.

Documentation of AEs/ARs will include AE description, start date and stop date, severity, relationship, action(s) taken, seriousness, and outcome.

When recording an AE, the following information should be provided on the trial AE CRF:

Action taken with trial intervention:

- None
- Trial intervention discontinued
- Trial intervention interrupted

AE outcome:

- Fatal
- Not recovered/not resolved
- Recovered/resolved
- Recovered/resolved with sequelae
- Recovering/resolving
- Unknown/lost to follow-up

Further details on assessing severity and causality of AEs and SAEs are in Appendix 14.

9.4.5 Follow-up of AEs and SAEs

If an AE/SAE is unresolved at the time of exit, efforts will be made to follow up until the AE/SAE is resolved or stabilized, the subject is lost to follow-up, or there is other resolution to the event. These follow-up visits will be documented.

The investigator is responsible for adequate and safe medical care of subjects during the study and for ensuring that appropriate medical care and relevant follow-up procedures are maintained after the study.

The investigator should provide the study sponsor with any new safety information (which includes new AEs and changes to previously reported AEs) that may affect the safety evaluation of the study treatment. For AEs that are unresolved/ongoing at time of subject exit from study, any additional information received at follow-up should be documented in the eCRFs up to study completion (i.e., database lock).

Any additional data received within 30 days after subject has stopped study participation (last visit or time of last dose of the study treatment taken (whichever is later) must be documented and available upon the study sponsor's request.

9.4.6 Reporting of SAEs

An investigator must immediately (i.e., within 24 hrs) report any SAE or SAR to the sponsor or sponsor representative, whether or not considered trial intervention-related, including those listed in the protocol or IB. The investigator must use the SAE report form (eCRF or email as a back-up) and include an assessment of whether there is a reasonable possibility that the trial intervention caused the event. The investigator must report any SAE or SAR that occurs or is observed during the trial. In case of incomplete information, the investigator must provide follow-up information as soon as possible, again using the SAE report form. The details for SAE/SAR report submission are listed below.

Report SAEs/SARs within 24 hrs via electronic data capture (EDC) system or, in the case of the EDC system not being available, the provided SAE source document will be completed and sent via the instructions noted on the form to the sponsor representative within the expected reporting time frame.

SAE/SAR reports will be evaluated by the medical monitor. Regulatory authorities, IRB/IEC, and investigators at each of the trial sites will be informed as required.

An assessment of seriousness will also be performed for all adverse events by a sponsor physician utilizing the same criteria. If an adverse event reported for an investigator's subject is upgraded to a serious adverse event by a sponsor physician, the investigator will receive a notification from the sponsor.

9.4.7 Regulatory Reporting Requirements for SAEs

This clinical study is being conducted exclusively in the US where the IP is considered an OTC monograph drug. As such, there are no regulatory requirements to report SAEs to the health authority. There are no IRB requirements for an OTC monograph drug.

9.4.8 Serious and Unexpected Adverse Reaction Reporting

An investigator must immediately (i.e., within 24 hrs) report SUSARs. In the event of SUSAR, the site must notify the medical monitor for the trial and submit an SAE report form in EDC within 24 hrs of notification, observation, or occurrence of the SUSAR, whether or not complete information is available to the sponsor or sponsor representative. In the case of

incomplete information, the investigator must provide follow-up information as soon as possible using the SAE report form.

9.4.9 Adverse Events of Special Interest

Not applicable to this study.

9.4.10 Disease-related Events or Outcomes Not Qualifying as AEs or SAEs

Any medical condition present prior to informed consent which remains unchanged or improved should not be recorded as an AE at subsequent visits. However, an AE should be recorded if the frequency, intensity, or the character of a preexisting condition worsens during the trial period beyond what would be expected from the natural progression of that condition.

Surgery should not be reported as an adverse event nor as an outcome of an adverse event if the purpose of the surgery was diagnostic and the outcome was uneventful.

If there is a question as to whether a medical development should be reported as an adverse event, it is recommended the investigator contact the sponsor for guidance.

9.5 Device Deficiencies

A device deficiency is inadequacy of a medical device with respect to its identity, quality, durability, reliability, safety, or performance. This definition includes malfunctions, use errors, and inadequacy in the information supplied by the manufacturer. A device deficiency may or may not be associated with patient harm (i.e., AE or SAE); however, not all AEs or SAEs are due to a device deficiency. The investigator should determine the applicable category listed in the Device Deficiency eCRF for the identified or suspect device deficiency and report any patient harm separately. Examples of device deficiencies include the following:

- Defective component
- Damaged package
- Mixed/mislabeled
- Potential contaminant
- Tampered seal
- Incorrect capping

- Partial seal
- Other (specify)

9.6 Pregnancy and Postpartum Information

Pregnancies occurring in subjects enrolled in the study must be reported and followed to outcome. No further study treatments will be administered to pregnant subjects; however, the subject will be encouraged to complete all visits in the study.

If a woman is of childbearing potential, she must have a pregnancy test performed at the Screening and/or Baseline visits prior to confirmation of eligibility (and prior to start of study treatment). Additional pregnancy tests may also be required per local regulatory guidelines. Subjects with a positive pregnancy test result must be excluded from the study. Subjects with a negative pregnancy test result must agree to use a highly effective contraception method during the study.

While pregnancy itself is not considered to be an AE, pregnancy reports are tracked by the sponsor or sponsor representative. The investigator must complete the Pregnancy Report Form and email or fax the form to the sponsor or sponsor representative. Following delivery or termination of the pregnancy, the Pregnancy Report Form is to be completed and sent by email or fax to the sponsor or sponsor representative.

Premature terminations including miscarriage, spontaneous abortion, or elective termination of a pregnancy for medical reasons will be reported as a serious adverse event (SAE). Other pregnancy complications should be reported as SAEs if they meet the seriousness criteria. Should the pregnancy result in a congenital anomaly or birth defect, a separate SAE must be submitted for the child. Furthermore, all neonatal deaths that occur within 30 days of birth, without regard to causality, should be reported as SAEs.

9.7 Device Deficiencies for Drug/Device Combination Products

N/A

9.8 Pharmacokinetics

N/A

9.9 Genetics

N/A

9.10 Biomarkers

N/A

9.11 Immunogenicity Assessments

N/A

9.12 Medical Resource Utilization and Health Economics

N/A

10 STATISTICAL CONSIDERATIONS

Continuous variables will be summarized using the number of observations, mean, standard deviation (SD), median, minimum, and maximum, as well as confidence intervals (CIs) or confidence limits (CLs) where applicable. Categorical variables will be summarized with frequencies and percentages from each category.

Unless otherwise specified, baseline will be defined as the last available measurement prior to IP exposure. Change from baseline will be calculated as postbaseline timepoint/visit value minus baseline value.

Final subject evaluability must be determined prior to locking the database, based upon the data evaluability plan (DEP).

The primary analysis will be conducted on the Safety Analysis Set ([Section 10.1](#)) at Day 30, for the change from baseline calculation.

Any deviations to the analysis plan will be updated during the course of the study as part of a protocol amendment or will be detailed in the clinical study report.

10.1 Analysis Set

Two analysis data sets will be defined.

Safety Analysis Set: includes all subjects/eyes exposed to at least one dose of IP.

Per Protocol (PP) Analysis Set: is a subset of the Safety Analysis Set and excludes all data meeting any of the critical deviation or evaluability criteria specified in the DEP.

10.2 Analyses Supporting Primary Objective(s)

[REDACTED]

The Safety Analysis Set will serve as the primary analysis set for the primary efficacy endpoint. [REDACTED]

[REDACTED]

[REDACTED]

[REDACTED]

10.2.1 Statistical Model, Hypothesis, and Method of Analysis

The null and alternative hypotheses for the analysis of the primary efficacy endpoint are:

$$H_0: \mu_{(T)} \geq 0$$

$$H_a: \mu_{(T)} < 0$$

where $\mu_{(T)}$ denotes the mean change from baseline in total IDEEL-SB score at Day 30.

A paired (one-sample) t-test will be used on the change from baseline value at Day 30 to test these hypotheses. One-sided p-value will be calculated, and null hypothesis will be rejected if p-value < 0.05.

[figure not shown]
In addition, descriptive statistics for observed and change from baseline values will be summarized.

[figure not shown]
10.2.2 Handling of Intercurrent Events of Primary Estimand(s)

The treatment-policy strategy will be used whereby all subjects exposed to at least one dose of IP, regardless of any ICE, will be included in the analysis. In addition, should an ICE result in a protocol deviation, data evaluability will be determined prior to final database lock and analysis will also be done on a per-protocol basis, as applicable.

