7.8.1 Prohibited Concomitant Therapy

The table below outlines all prohibited prior and concomitant therapies. Subjects must discontinue the use of any of the therapies or interventions listed in [Table 7-2](#) for the specified period prior to the specified visit and these therapies or interventions must not be used during the course of the study. Use of any of these therapies or interventions during the course of the study must be documented as a protocol deviation.

Table 7-2 Prohibited Concomitant Therapies

Intervention/Therapy	Washout Required	Precaution(s) and Action(s) to be Taken	Rationale
Topical ocular medications preserved with benzalkonium chloride. Examples include: Travatan, Xalatan, Lumigan, etc.	A month before the Screening visit until subject is exited from the study.	Discontinue subject from study if taken concomitantly during IP administration.	May confound primary efficacy variable.
Any artificial tear products. Examples of prohibited ocular lubricants include: Blink, Refresh, Biotrue, other Systane products, iVizia, Visine, Soothe, etc. See exclusion criteria number 14 (Section 6.3)	From the beginning of the Baseline visit until subject is exited from the study.	Discontinue patient from study if any ocular lubricant is taken concomitantly with IP for more than 2 consecutive days.	May confound primary efficacy variable.

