8.1.1 Criteria for Permanent Discontinuation of Investigational Product

A subject may be discontinued from IP at the discretion of the investigator or the medical monitor. Other reasons that a subject may be discontinued from IP may include, but are not limited to:

- *Adverse event(s) (AEs including, in the opinion of the investigator, clinically relevant laboratory abnormalities, and intercurrent diseases reported by the subject or observed by the investigator)
- ^Pregnancy

*AE may result in discontinuation of IP; however, it is up to discretion of the investigator if subject should continue safety assessments in the study.

^Pregnancies occurring in subjects enrolled in the study must be reported and followed to outcome. No further study treatments will be administered to pregnant subjects; however, the subject will be encouraged to complete all safety assessments in the study.

Subjects that discontinue IP and continue in the study should continue safety assessments.

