10.2.3 Handling of Missing Data Not Related to Intercurrent Events

All data obtained in evaluable subjects/eyes will be included in the analysis. No imputation for missing values will be carried out for the primary and key exploratory efficacy analysis.

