#### 4 EFFICACY ANALYSIS STRATEGY

This study defines 1 primary efficacy endpoint and [REDACTED]  
[REDACTED] will use the Safety Analysis Set as the primary analysis set. [REDACTED]  
[REDACTED]  
[REDACTED]

Continuous variables will be summarized using the number of observations, mean, standard deviation (SD), median, minimum, and maximum, as well as confidence intervals (CIs) or confidence limits where applicable. Categorical variables will be summarized with frequencies and percentages from each category.

Unless otherwise specified, baseline will be defined as the last available measurement prior to IP exposure. Change from baseline will be calculated as postbaseline timepoint/visit value minus baseline value.

[figure not shown]
All data obtained in evaluable subjects/eyes will be included in the analysis. [REDACTED]  
[REDACTED]  
[REDACTED]  
[REDACTED].

A listing of select efficacy data will also be provided.

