**Table 4-2 Summary of Analytical Strategy for Primary Endpoint**

[figure not shown]
Endpoint	Estimand Designation  (Primary/Supplementary/Sensitivity)	Analysis Set	Intercurrent Event	Intercurrent Event Strategy and Estimator (efficacy analysis)	Handling of Missing Data Unrelated to Intercurrent Events and Summary Measure
Change from baseline in IDEEL-SB questionnaire score at Day 30	Primary	Safety Analysis Set	Use of prohibited medication	Use data as collected	No imputation
			IP discontinuation	Use data as collected	No imputation

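### The primary estimand covers all dosed subjects under treatment policy, but the protocol does not reliably collect a Day 30 IDEEL-SB score after the named intercurrent events or, in the visible text, say how Early Exit scores are used

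*Protocol*

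**What the plan says.** **Estimand and test.** Protocol 4.2 names two kinds of intercurrent event: concomitant medication, and permanent or temporary discontinuation of IP. Protocol 10.2.2 handles them as follows: "The treatment-policy strategy will be used whereby all subjects exposed to at least one dose of IP, regardless of any ICE, will be included". SAP Table 4-2 lists use of prohibited medication and IP discontinuation, and for each says "Use data as collected" with no imputation. Protocol 10.2.3 adds: "All data obtained in evaluable subjects/eyes will be included in the analysis. No imputation for missing values will be carried out". The test (Protocol 10.2.1, SAP 4.3.1) is a one-sided, one-sample t-test at 0.05 on the change from baseline at Day 30.

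**What happens to subjects after an event.**
- Table 7-2, benzalkonium-preserved topical medication: "Discontinue subject from study if taken concomitantly during IP administration".
- Table 7-2, artificial tears: "Discontinue patient from study if any ocular lubricant is taken concomitantly with IP for more than 2 consecutive days".
- Section 8.1.1, permanent IP discontinuation: "Subjects that discontinue IP and continue in the study should continue safety assessments". If the cause is an adverse event, even this is left to the investigator.
- Section 8.1.2, interruption: subjects may be taken out of the study at the investigator's discretion, yet every effort is to be made to keep them in with the Table 2-2 assessments to the final visit.
- Pregnancy: Section 8.1.1 encourages all safety assessments, while Section 9.6 encourages all visits.

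**When the IDEEL-SB is collected.** Table 2-2 and Section 9.2.1 place it at Screening, Visit 4 and Early Exit. Section 8.2 holds the early exit visit where possible. Section 9.3.5 requires exit procedures, as possible, when a subject stops IP or leaves the study at an unscheduled visit.

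**The concern.** Treatment policy means that the outcome counts whatever happened after the event. It works only if the outcome is measured after the event, at the time the endpoint names. Here the sections on discontinuation tend to end or thin out follow-up after exactly the events that the estimand says to ignore.

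Two things follow. First, a dosed subject with no Day 30 score has no change value, so that subject drops out of the t-test. The reported mean then describes subjects with a score, not all dosed subjects. If those lost did worse, the reduction is overstated; if they did better, it is understated. Section 8.2 lists adverse events and lack of efficacy among the reasons for withdrawal, so loss related to outcome is plausible, but the documents do not show its direction. There is no control arm in which a similar loss might offset it.

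Second, an Early Exit score may exist, and two analysts could reasonably differ on whether it counts as Day 30. The study is open label and all staff are unmasked (Protocol 7.6.2), so that choice should be in writing before outcomes are seen.

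**Working it through.** **Step 1. Trace each event to a Day 30 score.**

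| Event | What the protocol directs | Day 30 score secured? |
|---|---|---|
| Benzalkonium-preserved drops | Off study (Table 7-2) | No; Early Exit score if possible |
| Ocular lubricant, more than 2 consecutive days | Off study (Table 7-2) | No; Early Exit score if possible |
| Ocular lubricant, 2 days or fewer | No discontinuation directed | Yes, at Visit 4 |
| Permanent IP stop, stays in study | Safety assessments named (8.1.1); Table 2-2 does not waive the IDEEL-SB | Unclear |
| Interruption | Removal at discretion, and every effort to retain (8.1.2) | Unclear |
| IP or study stopped at an unscheduled visit | Exit procedures then (9.3.5) | Score at that date only |

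The Visit 4 window is Day 30 ± 5, that is Day 25 to Day 35. An exit visit can fall well before Day 25.

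**Step 2. Does a stated rule admit the Early Exit score?** Section 9.2.1 groups Early Exit with Visit 4 for collection only. The instruction in SAP Table 4-2 does not settle it, because the endpoint is fixed at Day 30. The no-imputation entries sit under headings about data missing for reasons unrelated to intercurrent events; no visible heading covers data missing because of one. No rule is visible.

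**Step 3. How many subjects could be affected?** SAP Table 1-1 gives a target of 143 completers and about 185 enrolled: 185 − 143 = 42, and 42/185 = 22.7%. No dropout rate is stated. Inflating 143 by a 22.5% loss gives 143/0.775 = 184.5, or 185, which is consistent but confirms nothing. The 42 is an upper bound on dosed subjects without a score. Protocol 6.2 counts enrolment from consent, so 42 may include subjects never dosed, whereas Table 1-1 of the protocol counts from first IP. Some of the 42 may also have a usable score.

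**Step 4. Bias in the mean (illustration).** Let f be the fraction missing and k the difference in mean change, missing minus observed. Observed mean minus all-dosed mean = −k × f. The documents give no k; assume 5 points worse.
- 9 missing: f = 9/185 = 4.9%; 5 × 0.0486 = 0.24 points
- 19 missing: f = 19/185 = 10.3%; 5 × 0.1027 = 0.51 points
- 42 missing: f = 22.7%; 5 × 0.2270 = 1.14 points

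If the missing do 5 points better, the sign reverses and the sizes are the same. Counting every missing subject as zero change turns an observed mean of −10 into −10 × (185 − missing)/185 = −9.5, −9.0 or −7.7.

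**Step 5. Could significance be lost (illustration)?** Assume SD 18 in both groups (no SD is visible). With n observed at mean c and m missing at mean x:
- M = (n·c + m·x)/185
- S² = [183 × 18² + n(c − M)² + m(x − M)²]/184
- t = M/(S/√185), against a critical value of −1.653

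Example with 42 missing, c = −10, x = 22: M = (−1430 + 924)/185 = −2.74, S = 22.4, S/√185 = 1.65, t = −1.66, which is just at the limit.

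| Observed mean | Tipping x, 19 missing | Tipping x, 42 missing |
|---|---|---|
| −10 | +55.6 | +22.0 |
| −5 | +20.5 | +7.0 |
| −3 | +4.8 | +0.6 |

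An observed mean of −10 is hard to overturn. Only a small effect with heavy loss is fragile.

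**The case against.** The strongest reply is that the protocol collects more than this suggests. Section 8.1.1 does not waive the IDEEL-SB, Table 2-2 schedules it at Visit 4 and Early Exit without exempting subjects off IP, and Section 9.6 encourages pregnant subjects to complete all visits. Lubricant use of 2 days or fewer does not remove anyone. No imputation is a disclosed choice. All of this stands, and it limits the point: the score is not reliably collected, which is different from being ruled out. It does not remove the point, because subjects discontinued from the study have no scheduled Day 30 contact, and Sections 8.1.1, 8.1.2 and 9.6 give sites differing instructions.

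A reader might infer three stronger things that the documents do not support.
- **That the word evaluable lets dosed subjects be removed from the primary analysis.** SAP 4 does say "All data obtained in evaluable subjects/eyes will be included in the analysis", but Protocol 10.1 and SAP 2.2 apply the data evaluability plan's exclusions to the Per Protocol set, and the Safety Analysis Set is primary.
- **That the plan has no sensitivity analysis and no Early Exit rule.** Text in Protocol 10.2 and SAP 4 is redacted, the Table 4-2 header provides for supplementary and sensitivity estimands whose rows may not be visible, and the data evaluability plan is not in the documents.
- **That the trial's error rate is inflated.** That needs a true mean change of zero, an SD, a gap and a missing count, none of which the documents give.

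It is also fair that post-exit follow-up is new and cannot recover subjects who are lost or who withdraw consent.

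**Conclusion.** The point holds in this form: the estimand is all dosed subjects under treatment policy, but the visible protocol does not reliably collect the Day 30 score after the events that the estimand covers, and no visible text says whether an Early Exit score enters the Day 30 test. The primary t-test may therefore be an available-case analysis whose mean need not be the quantity that 10.2.2 defines.

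The direction of bias is unknown. At an assumed 5-point gap its size is about 0.2 to 1.1 points for 9 to 42 missing; the gap, the SD of 18 and the missing counts are all assumptions, and 42 is an upper bound. A large observed effect would stay significant, so the gain is a less biased estimate of the stated estimand and probably not a different test result. The mismatch between the discontinuation sections and 10.2.2 is visible without any redacted text; the Early Exit gap is conditional on what the redactions and the data evaluability plan contain. It is worth fixing because the remedy is cheap.

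**What to change.** 1. In Protocol 8.1.1 and Table 2-2, ask each dosed subject who stops IP or exits early, and who agrees, to complete the IDEEL-SB by ePRO in the Day 30 ± 5 window, and use that score in the primary test. Footnote 8 of Table 2-2 already makes the questionnaire an ePRO.
2. In SAP 4.3.1, state that an Early Exit score counts as Day 30 only if it falls within Day 30 ± 5, unless the redacted text or the data evaluability plan already sets a rule.
3. Reconcile Table 7-2 and Sections 8.1.1, 8.1.2 and 9.6 with 10.2.2, so that sites have one instruction on which assessments continue after each event. No clinical rule on stopping or retention is proposed here.

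**Cost.** A short amendment to protocol and SAP, and one remote questionnaire after stopping or exit for at most about 42 subjects. This is follow-up that the present schedule does not contain, and it will not recover subjects lost to follow-up or those who withdraw consent. The reported mean reduction may turn out smaller.
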